The quality of life questionnaires have become of recent interest. Although the BCTQ and VAS score are able to scale functional disability and pain, they are not constructed to determine the quality of life which encompasses emotional and social domains of everyday function. The SF 36 measures two distinct physical and mental dimension. It also can good validity and reproducibility and is useful in our clinical setting (22).

Randomisation

Patients' randomisation is done by an independent statistician using a random number generating programme (www.randomizer.org) into two groups (treatment and placebo) using mixed block randomization technique at the ratio of 1:1 i.e. group A and group B. The independent statistician will then code the treatment and the placebo into group A and group B. The written allocation of assignment for each participant with an identification number (code) was sealed in a brown opaque envelope. This envelope will be opened by the researcher on recruitment of a participant. The key coding to the allocation will be revealed by the independent statistician at the completion of the study. An independent statistician will label the treatment and placebo group as either group 'A' or group 'B'.

The participants are assigned to either treatment or placebo arm in a parallel intervention mode.

The principle of random allocation is employed to assign the participants to an intervention (i.e. treatment) and a control (i.e. placebo arm). To achieve an unbiased comparison group and to have a balanced randomization, permuted block randomization with a varying block size is used for the study. The sample size estimated for the study is 76. Hence, there are 19 blocks with a block size of four participants each and one-to- one allocation ratio is used. Random sequence generation is done with the help of a Research Randomizer, an online random number generator (Urbaniak & Plous, 2014). An external member, who is not directly involved in the study, generates the sequence. To have a strict implementation of the generated random sequence, the concealed allocation is achieved using sequentially numbered, opaque and sealed envelopes (SNOSEs). An aluminium foil is kept inside the envelope to prevent possible chances of deciphering. An external member, who is not directly involved in the study, would prepare the SNOSEs.

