The final code is only known to the statistician and the document will be stored in a secure locked safe. The following information will be recorded during the randomization; study ID (assigned during the study initiation), investigator password (assigned during the initiation), subjects screening status, date of informed consent signed by subject, subject's ID no (e.g., Last 4 digits of IC), upon successful randomization, the subjects will be assigned randomization number and treatment. The subject's ID no. and randomization no. will be documented on the Patient Enrolment Log and Patient Identification List.

Blinding and emergency unblinding procedures

The participants and outcome assessor of the study is blinded about the allocation status of the participants. In the setting of an adverse event (AE), for which knowledge of the identity of the test drug is necessary to manage the subject's condition, the sealed emergency code key for that subject may be broken and the test drug identified by the medical monitor. The medical monitor will have a set of sealed emergency code keys (one for each subject) kept in a secured location and he/she will be accessible at all times by telephone. The medical monitor is medical officer who is working in the hospital. He/she is familiar with hospital system and is also aware of the study protocol. Should emergency code key for that subject, identify the test coil and inform the investigator. A detailed report with the date and reason for identifying the study drug will

be prepared by the medical monitor and attached to the case report form. This report must be signed by the medical monitor and the investigator. All unused sealed code keys will be accounted for at the end of the study.

Except in the case of emergency, the treatment blind will be maintained until all subjects have completed the treatment and the database has been cleaned and locked. Any broken code will be clearly justified and explained by a comment on the case report form, along with the date on which the code was broken.

Sample size estimation

Sample size calculation was performed using the study published by Pajardi et al. Sample size was calculated based on improvement to limitations of everyday activity among the patients with CTS as the outcome parameter (1.07 ± 1.27 vs 0.83 ± 0.81). The marginal error (α) was set at 0.05.

Sample size: $2 \frac{\text{SD}^2(2\alpha/2 + Z\beta)^2}{d^2}$

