SD – standard deviation = from previous studies or pilot study $Z\alpha/2 = Z \ 0.05/2 = Z \ 0.025 = 1.96$ (From Z table) at 80 % power at type 1 error of 5 % $Z \beta = Z \ 0.20 = 0/842$ (From Z table) at 80 % power d= effect size = difference between mean value

So, the formula: sample size: $2 \cdot SD^2(1.96 + 0.84)^2$ d^2 SD = 1.27 Za/2 = 1.96 Zb = 0.84 $d^2 = (0.81)^2 = 0.66$ $n = \frac{2(1.27)^2 (1.96 + 0.84)^2}{(0.81)^2}$

= 2 (1.61) (7.84)

0.66

= 38 in each arm (Total 76 patients)

Operational definitions

Primary outcome measure

The primary outcome was the electrodiagnostic improvement of the median nerve on NCS before the before the intervention (visit 1) and at three-months (visit 2) and six- months (visit 3). The NCS parameters that are analysed were:

- 1. Distal sensory latency; DSL (normal value for DSL <3.5ms)
- 2. Sensory nerve action potential; SNAP (normal value for SNAP >2.5 μ V)
- 3. Conduction velocity; CV (normal value for CV >50m/s)
- 4. Distal Motor Latency; DML (normal value for DSL <4ms)
- 5. Compound muscle action potential; CMAP (normal value for CMAP>4.0 mV).

Secondary outcomes measures

- Tolerability and safety of oral combination of alpha lipoic acid and vitamin B preparations
- The improvement of scores in Boston Carpal Tunnel Questionnaires (BCTQ) by the SSS scale prior to the intervention, at 3 months and at 6 months
- The improvement of scores in Boston Carpal Tunnel Questionnaires (BCTQ) by the FSS scale prior to the intervention, at 3 months and at 6 months
- The improvement of pain scores in VAS prior to the intervention, at 3 months and at 6 months
- The improvement of quality of life score SF 36 prior to the intervention, at 3 months and at 6 months

Data collection

[figure not shown]
Protection of human rights is the utmost priority for researchers. We obtain informed consent from all participants in this research. The consent process included giving full and comprehensible information about the research and clear assurance of their voluntary

participation. Beneficence is the essence of concern for the well-being of the participants whereby the risk of harm was the least possible.

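### The formula's 38 per arm counts patients with an outcome but is used as the number randomised, with no allowance for six months' loss, so the stated 80% power is not delivered even on the inputs as entered

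*Combined protocol and SAP*

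**What the plan says.** Section 9, Sample size estimation, applies the usual two-means formula. Alpha is given as "The marginal error (α) was set at 0.05", the power as "at 80 % power at type 1 error of 5" per cent, and the values entered are "SD = 1.27 Za/2 = 1.96 Zb = 0.84" with d = 0.81. The result is "38 in each arm (Total 76 patients".

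Section 9, Randomisation, carries the total over unchanged: "The sample size estimated for the study is 76. Hence, there are 19 blocks with a block size of four participants each".

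Study procedure puts the follow-up visits at three and six months, with a call and a reminder message at weeks 6 and 18. Section 10 keeps every randomised subject in the analysis by intention to treat. The available text gives no expected loss rate, no inflation step, no rule for replacing withdrawn patients and no method for missing outcome values.

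**The concern.** A sample size formula for two means returns the number of patients whose outcome is measured. If the same number is randomised, the stated power requires that nobody is lost. Here nobody may be lost over six months, in a trial whose primary outcome needs attendance for nerve conduction studies. There is also no slack, because the formula result was rounded down.

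A null result would be read against an unconditional 80%, although the evaluable trial is likely to be smaller than the one that figure describes. This problem is separate from the choice of inputs: correcting d would still leave the plan with no step for loss.

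**Working it through.** **Inputs.** SD 1.27, d 0.81, z values 1.96 and 0.84, and 1:1 allocation, all from section 9. The documents give no loss rate. About 10–20% is assumed.

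**1. The plan's own figure.** n = 2·SD²·(1.96 + 0.84)² / d² per arm.
- With the plan's rounded terms: 2 × 1.61 × 7.84 / 0.66 = 38.25.
- Without intermediate rounding: 2 × 1.27² × 2.8² / 0.81² = 38.55.

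The 38 is therefore reproduced to within one patient, as a number with an outcome and with no term for loss. Rounded up, it would be 39. The list holds 19 × 4 = 76 = 2 × 38 allocations, so there is no reserve.

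**2. Power with full retention.** By the normal approximation, power = Φ(d / (SD·√(2/n)) − 1.96). At n = 38 this is Φ(0.81 / (1.27 × 0.2294) − 1.96) = Φ(0.82) = 79.4%. The two-sample t-test (noncentral t) gives 78.3%. The gap below 80% at this stage comes from rounding down and from using t in place of z, not from loss.

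**3. Power after loss, on the inputs as entered.** Detectable effects are for 80% power by t-test. The planned effect is 0.81 / 1.27 = 0.64 SD.

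| Evaluable per arm | Loss from 38 | Power, t-test | Power, normal | Detectable effect |
|---|---|---|---|---|
| 38 | 0 | 78.3% | 79.4% | 0.65 SD |
| 37 | 1 (2.6%) | 77.2% | 78.3% | – |
| 36 | 2 (5.3%) | 76.1% | 77.2% | – |
| 34 | 4 (10.5%) | 73.6% | 74.8% | 0.69 SD |
| 32 | 6 (15.8%) | 70.9% | 72.3% | 0.71 SD |
| 30 | 8 (21.1%) | 68.1% | 69.5% | 0.74 SD |

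For 34 to 30 evaluable per arm, the shortfall against 80% is 80 − 73.6 = 6.4 to 80 − 68.1 = 11.9 points. The part due to loss is 78.3 − 73.6 = 4.7 to 78.3 − 68.1 = 10.2 points.

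**4. What the inputs as entered are worth.** The plan defines d as "effect size = difference between mean value" and quotes the source result as "1.07 ± 1.27 vs 0.83 ± 0.81". The difference in means is 1.07 − 0.83 = 0.24; the 0.81 is the second group's SD. With d = 0.24 and SD 1.27, the normal approximation gives:
- 38 per arm: Φ(0.24 / (1.27 × 0.2294) − 1.96) = Φ(−1.14) = about 13%
- 34 per arm: about 12%
- 30 per arm: about 11%

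The plan's formula would then need 2 × 1.27² × 7.84 / 0.24² = 439.1, so 440 per arm.

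**The case against.** **The power table rests on a wrong d.** This is the strongest objection, and it stands. A reader might take 68–74% as the trial's actual power. The documents do not support that: on the plan's own definition of d, power is about 13% before any loss, and loss then costs 1–2 points. The outcome used for sizing, limitation of everyday activity, is also not the nerve conduction primary outcome. The table shows only what the missing allowance does to the calculation as written, and printing it uncorrected would replace one misleading figure with another.

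**The size depends on an assumed loss rate.** This also stands. One patient lost per arm costs about 1 point, and the contacts at weeks 6 and 18 may limit loss. They do not justify planning for none.

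**Month 6 is not the only assessment.** A reader might infer that only month-6 completers count, or that recruitment beyond 76 is barred. Neither is stated. The primary outcome covers months 3 and 6, and the plan does not forbid replacement. A repeated-measures model could recover part of the information from month 3, but none is specified.

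**All randomised subjects are analysed.** That defines who is in the analysis. It does not supply outcomes that were never measured.

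**An allowance might be in a missing figure.** The data-collection figure and the flowchart content are not available. The sample size text is intact, however, and Randomisation uses the unadjusted 76.

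**The sample size is called adequate in section 10.** A reader might take this as a power claim that loss to follow-up refutes. Under Baseline Comparability it refers to balance between the groups at randomisation, which later loss does not affect.

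**Conclusion.** The point holds. The plan randomises the number that its formula requires with outcomes, allows nothing for loss, and states 80% power without condition. On the inputs as entered, that power is narrowly missed with full retention (78% by t-test, 79% by normal approximation). It is missed by about 6–12 points at 34 to 30 evaluable per arm, of which about 5–10 points are due to loss. The direction needs no assumption, since any loss lowers the power; the size rests on an assumed loss of about 10–20%. The wrong d is the larger problem, and an allowance for loss would not by itself make the sample size valid.

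**What to change.** Keep 76 patients and remove the unconditional 80% statement. In this order:

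1. Correct d to match the plan's own definition, or justify another value and its source.
2. Replace the closing lines of Sample size estimation with text such as: *Seventy-six patients are randomised, 38 per arm. With 38, 34, 32 and 30 evaluable per arm (no loss, and losses of about 10, 15 and 20%, assumed), power at two-sided 5% is a, b, c and d%, conditional on a difference of [value] and an SD of [value].* Compute the percentages only after step 1. With d = 0.24 and SD 1.27 they would be about 13% at 38 per arm and 11–12% at 34 to 30.
3. State that the calculation is for limitation of everyday activity and does not give the power for the nerve conduction primary outcome.

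Leave the adequate sample size wording under Baseline Comparability out of this change.

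The change needs no extra patients and alters no procedure. Its cost is a less favourable stated power: about 6–12 points below 80% on the inputs as entered, and far more once d is corrected. Inflating the randomised number on the present inputs is not a substitute. From 39 evaluable per arm, 10–20% loss would require 39/0.90 to 39/0.80, that is 44 to 49 per arm (88 to 98 in total), all still resting on d = 0.81.

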Of late, alpha lipoic acid (ALA) has gained interest due to its powerful scavenging activity, to metabolic support of nerve cells, as well as modulation of neurotrophic cytokines release. All together, these mechanisms reduce inflammation, improve functioning of the nerve fibers and promote neuroprotection and neuroregeneration (11,12). In a study involving rats, administration of ALA has shown to reduce infarct size, thus demonstrating its neuroproliferative and neurorestorative benefits. In this study, treatment with ALA increased proliferative cell lineage by 5 fold (13). Another study established neuroprotective property of ALA by means of increased expression of the proliferating cell nuclear antigen, which is a key regulatory protein for DNA repair. This study also exhibited anti-apoptotic of ALA against neurotoxicity which is a key aspect in cellular functioning (14).

This has led to the hypothesis of improved outcome if the medications are combined in a single preparation. As such, Bionerv was developed as a combination drug (Alpha Lipoic Acid (300mg), Methylcobalamin (500mcg), Vitamin B1 (39mg) and Vitamin B6 (8mg)) to simplify administration for patients. We would like to determine the efficacy of oral combination of alpha lipoic acid and vitamin B preparations versus placebo; with regards to symptom control and improvement on NCS parameters. Both groups are allowed to undergo physiotherapy which includes splinting, ultrasound and other non-pharmacologic treatment, as determined necessary by the clinician. The concomitant treatment that the patient is receiving is also recorded.

8. Conceptual framework

Intervention : Bionerv

AlphaLipoicAcid(300mg),Methylcobalamin(500mcg),VitaminB1(39mg)andB6(8mg);two tablets once daily.

Placebo : Maltodextrin, Microcrystalline Cellulose , Tricalcium Phosphate , Silicon Dioxide , Magnesium stearate; two tablets once daily.

Independent variable

Age

Gender

Anthropometric data

(weight, height, body mass index)

Comorbidities

Severity of CTS

Laterality of CTS

Primary outcome

Electrodiagnostic improvement of median nerve on NCS:

- i- Distal sensory latency (DSL)
- ii- Sensory action potential (SNAP)
- iii- Conduction velocity (CV)
- iv- Distal motor latency (DML)
- v- Compound Motor Action Potential (CMAP)

Secondary outcome

Tolerability of oral combination of alpha lipoic acid and vitamin B preparations

Boston Carpal Tunnel Questionnaires (BCTQ)

i-symptom severity scale (SSS)

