Privacy of patients are obtained in a respectful manner whereby every patient is given the confidence to directly disclose information to the researcher in a peaceful and non-threatening manner. Data collection sheets and questionnaires will not contain patients identification such as name, IC number, phone number, address or RN. Specific ID was used on the data collection sheet to ensure patient privacy.

All information obtained in this study will be kept and handled in confidential manner, in accordance to applicable laws and regulations of the country. Data management will be conducted using appropriate database and validation programmes, with standard practice to secure information for all computer based data storage (i.e encryption and password protection). Data collected may be retained for re-use in further studies. The standard duration of three to five years with strict security of research records will be adhered and destroyed after this period of time. Relevant bodies such as JKEUPM will have access to the study data.

Study flowchart

10. Data analysis

Analyses sets

All randomised subjects will be included in the analysis.

Baseline Comparability

True randomisation, concealed location and adequate sample size planned for this study will ensure enough baseline comparability between groups (treatment and control group). Additionally, a table of baseline characteristics of participants in each group, without betweengroup statistical comparisons will be included. This data will be analysed to determine whether any characteristics were imbalanced enough to have influenced the outcomes of the study

Efficacy Analysis

Analyses were performed on an intention-to-treat basis. The primary treatment comparisons of benefit include all eligible patients. Both eligible and ineligible patients are included in the analyses and compared by treatment assignment when an intent-to-treat analysis is specifically indicated.

Safety Analysis

The summaries of tolerability include all patients who received any study treatment; those who did not receive study treatment are not included in these summaries. The safety population comprised all randomized patients who received at least one treatment dose and was based on the actual treatment received.

11. Ethical consideration

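### The primary outcome is five unranked NCS parameters at two visits with no test, success rule or multiplicity adjustment, so the error rate of the primary claim is neither controlled nor known

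*Combined protocol and SAP*

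**What the plan says.** Section 8 (Conceptual framework) gives the primary outcome as "Electrodiagnostic improvement of median nerve on NCS" and lists five parameters beneath it: DSL, SNAP, CV, DML and CMAP. It names no visits.

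Section 9 (Operational definitions, Primary outcome measure) repeats this: "The primary outcome was the electrodiagnostic improvement of the median nerve on NCS". It compares the pre-treatment visit with later assessments "and at three-months (visit 2) and six- months (visit 3). The NCS parameters that are analysed were", then lists the same five with a normal limit for each. The numbers 1 to 5 only itemise the list; nothing ranks one parameter or visit above another.

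Section 10 (Efficacy Analysis) says: "Analyses were performed on an intention-to-treat basis. The primary treatment comparisons of benefit include all eligible patients". It adds that intention-to-treat analyses compare patients by assigned treatment. The rest of section 10 covers the analysis set, baseline comparability and the safety population.

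The only significance level, 0.05, is in section 9 (Sample size estimation). It applies to a single comparison on limitation of everyday activity, which is not an NCS parameter.

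**The concern.** A confirmatory trial needs its primary question to have one answer, reached by a rule fixed in advance. Four things are open here:

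- **What improvement means.** It could be a mean change, reaching the listed normal limit, or a change in severity grade.
- **Which parameters must improve.** It could be one, some or all five.
- **Which visit counts.** It could be month 3, month 6 or either.
- **How it is tested.** No model, significance level or adjustment is given for the primary outcome.

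The number of primary comparisons is five if each parameter is tested once (at one visit, or by one test across visits) and ten if each visit is tested. With no rule written, one could be chosen after the results are known. A chance difference on one parameter could then be presented as efficacy, and a reader could not say how often that would happen with an inactive product.

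**Working it through.** **1. The plan's own figure.** Section 9 uses n = 2·SD²·(1.96 + 0.84)²/d² with SD = 1.27 and d = 0.81. With its rounded inputs, 2 × 1.61 × 7.84 / 0.66 = 38.25, which agrees with the stated 38 per arm. The value 1.96 shows that this covers one comparison at two-sided 0.05. It makes no allowance for several primary comparisons.

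**2. Inputs for the error rate.** There are five parameters and two post-baseline visits (section 9, Primary outcome measure). Assumed: nominal two-sided 0.05 per test, no true effect, and test statistics that are jointly normal with the same correlation in every pair. The documents give no correlations, so 0 to 0.9 is an illustrative range.

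**3. If any one result were enough, independent tests.**
- Five tests, two-sided: 1 − 0.95⁵ = 0.226
- Ten tests, two-sided: 1 − 0.95¹⁰ = 0.401
- Five tests, favouring treatment only: 1 − 0.975⁵ = 0.119
- Ten tests, favouring treatment only: 1 − 0.975¹⁰ = 0.224

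**4. The same rule with correlated tests** (simulation, 1,000,000 draws, every pair at correlation 0.9).

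| Tests | Two-sided (nominal 5%) | Favouring treatment (nominal 2.5%) |
|---|---|---|
| Five | 0.101 | 0.051 |
| Ten | 0.128 | 0.064 |

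If the 0.9 between parameters and the 0.9 between visits are instead multiplied, different parameters at different visits correlate at 0.81. The ten-test figures are then 0.139 and 0.070.

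**5. If all five had to favour treatment at one visit.** The rate is 0.0004, 0.002 and 0.008 at correlations 0.5, 0.7 and 0.9.

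**6. Cost of Holm adjustment.** The strictest step is 0.05/5 = 0.01 for five tests and 0.05/10 = 0.005 for ten. With 38 per arm, a two-sample t-test and 80% power, the detectable effect for one parameter is 0.651 SD at 0.05, 0.802 SD at 0.01 and 0.860 SD at 0.005. Under ANCOVA, read SD as the residual SD. These figures avoid the plan's d, because 0.81 is the second group's SD in the quoted source figures, where the means differ by 1.07 − 0.83 = 0.24.

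**The case against.** **No any-one rule is written.** This stands. A reader might infer that the trial has a false-positive rate of up to 40%. The documents do not support that: every inflated figure depends on a rule they neither state nor exclude, and an all-five rule would put the rate well below nominal. What can be said is that the rate is unknown and uncontrolled.

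**NCS parameters are correlated.** They may well be, and the ranges allow for it. Even with every pair at 0.9, the any-one rate is at least twice nominal.

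**The trial is blinded.** Under section 9, participants and the outcome assessor are blinded, only the statistician knows the final code, and, emergencies aside, the blind holds until treatment is complete and the database is locked. A reader might instead infer that staff could pick a favourable rule during the trial, since "The independent statistician will then code the treatment and the placebo into group A and group B" and, of each allocation envelope, "This envelope will be opened by the researcher on recruitment of a participant". That requires assuming that the envelope shows the A/B code. Even then, someone comparing A with B would not know which was active, so could not deliberately favour treatment. The documents do not show such a breach, and the point does not need one. "The key coding to the allocation will be revealed by the independent statistician at the completion of the study", and with no rule on file one could be chosen after that.

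**The missing figures might hold the rule.** The omitted data-collection figure and study flowchart are unlikely places for one. The analysis section is present as running text, with no sign of redaction.

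**Conclusion.** The concern holds. The primary outcome is five unranked parameters, assessed at two post-baseline visits, with improvement undefined and no test, lead parameter, lead visit, success rule or multiplicity adjustment. The false-positive rate of the primary efficacy claim is therefore neither controlled nor known.

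Under the assumptions above, an any-one rule would give about 10-23% for five tests and 13-40% for ten. Counting only results that favour treatment, against a nominal 2.5%, it would give about 5-12% and 6-22%. An all-five rule at one visit would give under 1% for correlations up to 0.9. These are illustrations of how much the unwritten rule matters. They are not estimates of this trial's error rate.

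This must be fixed, because without a rule the primary result cannot be read as positive or negative at a stated error rate.

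**What to change.** **Preferred**, before any comparison by group or by A/B code: name one parameter at one visit. Suggested text: *The primary endpoint is [one parameter] of the median nerve in [the analysed hand] at month 6. Improvement is the between-group difference in means at month 6, adjusted for the baseline value of that parameter (ANCOVA) and tested two-sided at 0.05. The trial succeeds only if the difference is significant and favours treatment. All other NCS parameters and all month-3 values are secondary.* If CV is chosen, say whether sensory or motor. State which hand is analysed in bilateral disease, since section 8 records "Laterality of CTS" but no analysed hand is named. Month 6 and ANCOVA are reasonable choices, not ones the documents dictate.

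**Alternative:** keep all five as primary at month 6 with the same ANCOVA. Claim success if at least one parameter favours treatment with Holm-adjusted p<0.05, and limit the claim to the parameters that meet it.

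**If by-group results have already been seen** (the title page gives completion in September 2024): report all ten comparisons with Holm adjustment over ten and label any lead endpoint post hoc.

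**Cost.** One endpoint needs no extra patients or visits, but four parameters lose primary status. Holm raises the effect detectable for a single parameter at the strictest step from 0.65 SD to 0.80 SD (five tests) or 0.86 SD (ten), if all 38 per arm are evaluable; no dropout allowance is stated. The chance of at least one Holm claim is higher if several parameters respond. Under either option no NCS parameter has a power justification, because the sample size rests on everyday-activity limitation.

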During visit 1, a thorough history and physical examination were done, and demographic data was collected. Afterward, the patients were required to answer three sets of selfadministered questionnaires: Boston Carpal Tunnel Questionnaire (BCTQ), Visual analogue score (VAS) and SF-36. The BCTQ is a specific questionnaire for assessing CTS that consists of two distinct scales, the Symptom Specific Scale (SSS) which has 11 items and the Functional Status Scale (FSS) containing 8 items. Each scale generates a final score ranging from 1 to 5, with a higher score indicating greater disability and poor symptoms control. BCTQ is a reliable questionnaire to assess CTS owing to its high cross-cultural adaptation and multilingual validity and reliability (17-18). The VAS is a visual scale with 0 scored as "no pain" and 10 as "worst pain imaginable" and serves as an excellent tool for pain score with excellent validity and reproducibility (19-20). The SF-36 is a quality-of-life questionnaire that comprises of 36 questions covering eight domains of health which are; Physical Functioning (PF), Role Limitations due to Physical Health, Role Limitations (RL) due to Emotional Problems (RE), energy/fatigue, emotional well-being, social functioning, pain, and general health (GH) where a higher score indicates a better outcome (21). After the administration of these questionnaires, they will be subjected for a nerve conduction study (NCS) to determine the severity of CTS. The NCS were performed by the same trained personnel to ensure consistency and accuracy. A Patient-Reported Questionnaire to monitor any side effects were used to assess the tolerability of the drugs.

The patients were reassessed at Visit 2 (3 months post-treatment) and Visit 3 (6 months post-treatment). During each visit, they underwent physical examination, NCS, and were required to complete the three sets of questionnaires (BCTQ, VAS, and SF-36). They were also required to fill in the form regarding the side effects of the treatments. The investigators made a phone call and sent reminder message at the 6th and 18th week to ensure compliance, medication adequacy and follow up review. During the study, patients were allowed to undergo the standard of care treatment at our center such as physiotherapy.

Fig. 1 The visual analogue scale (VAS).

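### The efficacy section names no between-arm model and no adjustment for the visit 1 value, although every continuous efficacy outcome is measured at visit 1

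*Combined protocol and SAP*

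**What the plan says.** Section 10 has four parts: analysis sets, baseline comparability, efficacy and safety. The Efficacy Analysis paragraph opens "Analyses were performed on an intention-to-treat basis. The primary treatment comparisons of benefit include all eligible patients" and adds that eligible and ineligible patients are "included in the analyses and compared by treatment assignment when an intent-to-treat analysis is specifically indicated". That settles the population and the comparison by assigned arm, and nothing further. The Baseline Comparability paragraph promises a descriptive table without between-group tests, then says "This data will be analysed to determine whether any characteristics were imbalanced enough to have influenced the outcomes of the study". It names no covariate and no rule.

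Section 9, Operational definitions, states "The primary outcome was the electrodiagnostic improvement of the median nerve on NCS" and lists five parameters (DSL, SNAP, CV, DML, CMAP) before treatment and at three and six months. The secondary outcomes follow the same pattern, for example "The improvement of pain scores in VAS prior to the intervention, at 3 months and at 6 months" and "The improvement of quality of life score SF 36 prior to the intervention, at 3 months and at 6 months". Improvement is not defined.

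Section 9, Study procedure, shows that the visit 1 values exist. At visit 1 "the patients were required to answer three sets of selfadministered questionnaires" (BCTQ, VAS, SF-36), and "After the administration of these questionnaires, they will be subjected for a nerve conduction study (NCS) to determine the severity of CTS". NCS and the same questionnaires are repeated at visits 2 and 3.

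Two other places come near the subject. Sample size estimation uses a formula for two means, with d defined as the difference between means, applied to improvement in everyday-activity limitation. Section 8 lists age, gender, anthropometry, comorbidities, severity and laterality as independent variables, but ties them to no analysis and does not list the visit 1 value of any outcome.

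**The concern.** With three measurements per patient and an undefined improvement, the arms could be compared on change from visit 1, on follow-up values alone, or on follow-up values adjusted for visit 1. The plan does not say which. These analyses use the same data but differ in precision. The sample-size text leans towards the first, unadjusted.

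What is at stake is precision and a defined primary comparison. In a trial of 76 patients, the visit 1 value of the outcome is the obvious covariate: it is recorded before treatment and already collected. A plan that leaves it out, or leaves it to a later judgement about imbalance, risks giving up information at no saving.

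**Working it through.** **Inputs from the documents.** 38 per arm, 76 in total; two-sided 5% (the formula uses 1.96); 80% power; source figures 1.07 ± 1.27 and 0.83 ± 0.81. All are in section 9, Sample size estimation.

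**Assumed, because the documents do not give it.** The correlation r between visit 1 and follow-up values, taken as 0.3 to 0.9, and the ratio k = visit 1 SD / follow-up SD, taken first as 1 and then varied. Outcomes are treated as normal.

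**1. The plan's own figure.** n = 2 × SD² × (1.96 + 0.84)² / d² = 2 × 1.27² × 7.84 / 0.81² = 38.5; with the plan's rounded terms, 2 × 1.61 × 7.84 / 0.66 = 38.2. The stated 38 per arm reproduces. The formula is an unadjusted comparison of two means and contains no correlation or covariate term. The 0.81 entered as d appears in the source figures as an SD, which is a separate point.

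**2. Variance of the treatment effect at one follow-up visit**, relative to the follow-up variance:
- follow-up value only: 1
- change from visit 1: 1 + k² − 2rk, which is 2(1 − r) when k = 1
- adjusted for visit 1: (1 − r²)(1 + 1/72), where 1/72 is the cost of estimating the slope with 76 patients (76 − 4 = 72)

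**3. Equal SDs (k = 1).** Adjusted/change = ((1 + r)/2)(1 + 1/72). Adjusted/follow-up = (1 − r²)(1 + 1/72).

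| r | adjusted/change | cut | adjusted/follow-up | cut |
|---|---|---|---|---|
| 0.3 | 0.659 | 34% | 0.923 | 8% |
| 0.5 | 0.760 | 24% | 0.760 | 24% |
| 0.8 | 0.913 | 9% | 0.365 | 64% |
| 0.9 | 0.963 | 4% | 0.193 | 81% |

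Simulation of 200,000 trials per r gave 0.659, 0.759, 0.911, 0.963 and 0.922, 0.758, 0.364, 0.193. In patient numbers, a change-score analysis would need 76 / ratio = 115, 100, 83 and 79 patients to match the adjusted analysis of 76.

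**4. Unequal SDs.** Since 1 + k² − 2rk = (1 − r²) + (k − r)², the change score is already optimal when k = r, and the ratio then peaks at 1 + 1/72 = 1.014.
- r = 0.8, k = 0.8: 0.36 × 1.0139 / 0.36 = 1.014
- r = 0.5, k = 0.6: 0.75 × 1.0139 / 0.76 = 1.001
- r = 0.3, k = 1.25: 0.91 × 1.0139 / 1.8125 = 0.509

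The gain over change scores can therefore be nil, with a loss of at most 1.4%, or as large as about 49% in the last case.

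**5. Can adjustment rescue the sample size?** The source difference is 1.07 − 0.83 = 0.24. These figures treat the SD as that of improvement, with k = 1 and r from 0.3 to 0.9.
- SD 1.27: noncentrality 0.24 / (1.27 × √(2/38)) = 0.824; power 12.8% unadjusted, 17.0% down to 13.2% adjusted.
- Pooled SD √((1.27² + 0.81²)/2) = 1.065: noncentrality 0.982; power 16.3% unadjusted, 22.3% down to 16.7% adjusted.

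It cannot.

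**The case against.** **The plan does give a hint.** Sample size estimation speaks of improvement and a difference between means. This is the best evidence of intent, and it stands. It is still not declared as the analysis, it concerns everyday-activity limitation rather than NCS, and what it implies is unadjusted.

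**Change scores are legitimate, and the gain may vanish.** Correct. Under randomisation each of the three analyses holds about 5% error. Eligibility excludes normal, severe and extreme NCS grades, so a visit 1 SD below the follow-up SD is plausible for NCS, which moves towards the nil-gain case in step 4. What remains is that r and k are unknown. Adjustment costs at most 1.4% in variance against change scores under these assumptions, while either unadjusted choice can lose far more.

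**Improvement may not mean a continuous change.** A normal limit is given for each NCS parameter, so a proportion normalised is possible. The figures above do not cover that reading. Nor do the documents literally say improvement from visit 1; that is only the natural reading.

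**Stronger readings that a reader might infer:**
- *That an unadjusted analysis would be biased.* Randomisation rules this out for any single prespecified comparison.
- *That the open choice inflates type I error.* If the smallest p of the three analyses were always reported, error per outcome would be about 9% to 10%. Nothing in the documents says this would be done. The blind holds until database lock, although that does not fix the model.
- *That the sentence on imbalance by itself inflates error.* It describes no procedure from which that could be shown.

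**Conclusion.** The point holds as one of precision and prespecification. Section 10 states no between-arm efficacy model and no visit 1 adjustment, nothing elsewhere supplies them, and the data needed are already collected. With 38 per arm and equal SDs, over an assumed r of 0.3 to 0.9, adjustment lowers variance by 34% to 4% against change scores and 8% to 81% against follow-up values. With unequal SDs, the ratio to change scores runs from 0.51 to 1.014 in the cases examined. All of this rests on assumed correlations and SD ratios, on normal continuous outcomes, and on one outcome at one visit with complete data.

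A reader might infer that adjustment would make the trial adequately powered. The source figures do not support that: power at the 0.24 difference stays near 13% to 22%, and those figures are not for an NCS outcome.

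**What to change.** In the Efficacy Analysis text, prespecify one model for each continuous efficacy outcome (DSL, SNAP, CV, DML, CMAP, BCTQ-SSS, BCTQ-FSS, VAS and each reported SF-36 score). Use a repeated-measures mixed model over visits 2 and 3 with arm, visit, arm-by-visit, the visit 1 value of the same outcome and its interaction with visit. For NCS, take the visit 1 value from the same hand. Report the between-arm difference at each visit with a 95% CI. With complete data and an unstructured covariance, this gives the same estimate at each visit as a separate ANCOVA, so the variance figures above carry over.

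Replace the sentence about judging imbalance from the observed data with this fixed covariate. Keep the descriptive baseline table without tests.

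**Cost:** free improvement. It takes wording and a standard model, with no extra patients, visits or measurements. Timing matters: the title page gives completion as 30 September 2024, and section 10 mixes past and future tense. If unblinded results have already been seen, report the adjusted analysis as not prespecified.

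The choice of hand, the primary visit and any binary normalisation outcome are separate points that this wording does not settle.
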